### 5.2.1. Elimination from Total vaccinated cohort (TVC)

Code 1030 (Study vaccine not administered at all) and code 900 (invalid informed consent or fraud data) will be used for identifying subjects eliminated from TVC.

**5.2.1.1. Elimination from ATP cohort for immunogenicity Excluded subjects**

A subject will be excluded from the ATP cohort for immunogenicity under the following conditions

Code	Condition under which the code is used
900	Questionable subject => Invalid informed consent or fraudulent data. In case informed consent is obtained retrospectively the subject is not eliminated.
1030	Study vaccine dose not administrated at all but subject number allocated => subjects enrolled but not vaccinated
1040	Administration of concomitant vaccine(s) forbidden in the protocol Previous vaccination containing diphtheria, tetanus or pertussis antigens or diphtheria and tetanus toxoids at any time during the current pregnancy.
1050	Randomisation failure (subject who received a vaccine not compatible with randomization)
1060	Randomisation code broken at the investigator site OR at GSK Safety department
1070	Site or route of study vaccine administration wrong or unknown.
1080	Vaccine has been administered (effective treatment number) despite a temperature deviation qualified by Status QA GMP NON Use.
1090	Vaccine has been administered (effective treatment number) out of the expiration date at the time of administration.
2010	Protocol violation linked to the inclusion/exclusion criteria including age and excluding codes mentioned below.
2040	Administration of any medication forbidden by the protocol
2050	Underlying medical condition forbidden by the protocol
2060	Concomitant infection related to the vaccine which may influence immune response
2070	Concomitant infection not related to the vaccine which may influence immune response
2090	Blood sample taken but non-compliance with blood sampling schedule for the cord blood sample (dates of BS not corresponding to adapted protocol intervals or unknown BS/vaccination dates) => Cord blood should be at least 21 days after vaccination
2100	Serological results not available for all antigens from the cord blood sample
2120	Obvious incoherence, abnormal serology evolution or error in data in cord blood sample (incoherence between CRF and results, wrong sample labelling.

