5.3. Method of blinding

Data will be collected in an observer-blind manner. By observer-blind, it is meant that during the course of the study, the vaccine recipient and those responsible for the evaluation of any study endpoint (e.g. safety, reactogenicity) will all be unaware of which vaccine was administered. To do so, vaccine preparation and administration will be done by authorised medical personnel who will not participate in any of the study clinical evaluation assays.

The laboratory in charge of the laboratory testing will be blinded to the treatment, and codes will be used to link the subject and study (without any link to the treatment attributed to the subject) to each sample.

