10.4.3. ATP cohort for analysis of immunogenicity

The ATP cohort for analysis of immunogenicity will include all evaluable subjects from the ATP cohort for analysis of safety:

- Who meet all eligibility criteria.
- Who comply with the procedures and intervals defined in the protocol.
- Who are within the maximum interval allowed as defined in the protocol.
- Who do not meet any of the criteria for elimination from an ATP analysis (refer to Section 6.7.2) during the study.
- Who did not receive a product leading to exclusion from an ATP analysis as listed Section 6.7.2.
- Who did not present with a medical condition leading to exclusion from an ATP analysis as listed Section 6.8.
- Who have the cord blood collection at least 21 days post-vaccination.
- For whom data concerning immunogenicity endpoint measures are available. This will include subjects for whom assay results are available for antibodies against at least one study vaccine antigen component one month after vaccination i.e. Visit 3 in the cord blood sample.

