## 4. ENDPOINTS

### Primary

- Immunogenicity with respect to components of the study vaccine, at delivery (in cord blood sample):
  - Anti-PT, anti-FHA and anti-PRN antibody concentrations.

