## **6.3. Immunogenicity**

### **6.3.1. Analysis of immunogenicity planned in the protocol**

The primary analysis will be based on the ATP cohort for analysis of immunogenicity. If, in any vaccine group, the percentage of vaccinated subjects with serological results excluded from this ATP cohort is 5% or more, a second analysis based on the TVC will be performed to complement the ATP analysis.

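### SAP code 2120 lets an undefined judgement about the cord-blood serology, which is the primary endpoint, decide who is in the primary cohort; the bias could go either way

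*SAP*

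**What the plan says.** SAP 5.2.1.1 lists the codes under which a subject is excluded from the ATP cohort for immunogenicity. Code 2120 reads "Obvious incoherence, abnormal serology evolution or error in data in cord blood sample", followed by two illustrations in parentheses: "incoherence between CRF and results, wrong sample labelling". No threshold, comparison value or decision-maker is given for the serology ground.

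SAP 6.3.1 states: "The primary analysis will be based on the ATP cohort for analysis of immunogenicity". SAP Section 4 and Protocol 10.1 define the primary endpoint as the anti-PT, anti-FHA and anti-PRN concentrations in cord blood.

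Protocol 10.4.3 and SAP 5.1.3 define the cohort by eligibility, intervals, forbidden products, medical conditions, timing ("Who have the cord blood collection at least 21 days post-vaccination") and availability of results. The general bullet in Protocol 10.4.3, "Who do not meet any of the criteria for elimination from an ATP analysis (refer to Section 6.7.2) during the study", points to a list of concomitant products. SAP Section 9 and the three sections it refers to for other changes (6.1.2, 6.3.2, 6.4.2) do not mention code 2120.

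The one planned check is conditional (SAP 6.3.1). If, in any group, "the percentage of vaccinated subjects with serological results excluded from this ATP cohort is 5% or more, a second analysis based on the TVC" is added to complement the ATP analysis.

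**The concern.** Evolution of serology is most naturally read as the course of concentrations from Visit 1 through Visit 2 to cord blood, so it is judged from the values themselves. A vaccinated woman with no rise, or a placebo recipient with one, may be a true result that belongs in the comparison. Dropping such women makes the primary cohort depend on the primary outcome.

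The stake is the GMC ratio and the criterion that its lower 95% limit is at least 1.5. A small number of code 2120 cases would not by themselves reach 5% in a group, so no analysis that keeps these women need appear in the report.

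**Working it through.** **Inputs.** From Protocol 10.3 and Table 16: 272 evaluable women per group, anti-PT log10 SD 0.577, planned ratio 2.3, margin 1.5, one-sided alpha 0.025, stated power 96%. From SAP 6.3.1.2: Welch interval on the log10 scale. The documents give no count of code 2120 exclusions, so the counts below are assumptions.

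**1. The plan's own figure.** SE = 0.577 × √(2/272) = 0.0495. Distance from the margin = log10(2.3) − log10(1.5) = 0.1856. Power = Φ(0.1856/0.0495 − 1.96) = Φ(1.79) = 96.3%. The stated 96% reproduces.

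**2. Pass boundary.** The smallest observed anti-PT ratio that passes is 1.5 × 10^(1.964 × 0.0495) = 1.88.

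**3. Worst-case shift.** Suppose the lowest fraction p of dTpa cord values and the highest fraction p of Control values are removed. Each arm's mean moves by SD × φ(z)/(1 − p), with z the upper p quantile, and the two shifts add.
- p = 1%: 0.577 × 0.0267/0.99 = 0.0155 per arm; ratio × 10^0.031 = × 1.07.
- p = 2%: 0.0285 per arm; ratio × 1.14.
- p = 4.9%, just below the trigger: ratio × 1.33.

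**4. Simulated effect at a true ratio of 1.5** (anti-PT, SD 0.577, 272 per arm, Welch lower limit, 4,000 runs per row). The arm-aware and blind-on-change rows assume a correlation of 0.6 between pre-vaccination and cord values where change is used.

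| How women are removed | Number | Mean ratio | Chance of passing |
|---|---|---|---|
| None | 0 | 1.50 | about 2.5% |
| Arm known, extreme cord values | 3 per arm | 1.62 | about 11% |
| Arm known, extreme cord values | 13 per arm | 1.97 | about 72% |
| Arm known, extreme change | 3 per arm | 1.55 | 5.5% |
| Arm known, extreme change | 13 per arm | 1.69 | 19% |
| Blind, extreme change | 3 per tail | 1.48 | 1.8% |
| Blind, extreme change | 13 per tail | 1.44 | 1.0% |
| Blind, extreme cord values | 3 per tail | 1.46 | 1.4% |
| Blind, extreme cord values | 13 per tail | 1.37 | 0.4% |

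Thirteen of 272 is 4.8%, so 13 per arm is about the most that stays below a 5% trigger if no other code excludes anyone with results.

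**5. At the planned anti-PT ratio of 2.3.** With 3 per arm removed and the arm known, power rises from 96% to 98–99%. With 3 per tail removed blind, it falls to about 93–94%; with 13 per tail, to about 71–85%. Blind use is therefore not harmless, since it costs power and biases the estimate downward.

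**The case against.** The strongest reply is that this is a data-quality code. Both illustrations are record or labelling errors, the entry opens with obvious incoherence, and the serology ground may only mean results that point to a swapped sample. That reading is possible. But the ground is separately listed and joined by an or, and the text does not confine it to proven errors. If errors are all that is meant, the other two grounds already cover them.

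A second reply is blinding. Protocol 5.3 says "The laboratory in charge of the laboratory testing will be blinded to the treatment"; Protocol 5.4.1 says sponsor and study staff are blinded; the glossary places unblinding after data cleaning. This has real force. A reader might infer that the code inflates the ratio, on the view that concentrations give away the arm. The documents do not support that. At the planning values the anti-PT arms differ by log10(2.3)/0.577 = 0.63 SD, so one cord value identifies the arm correctly about Φ(0.31) = 62% of the time; for FHA or PRN (ratio 5, SD 0.564) it is about 73%. Combining antigens or adding pre-vaccination values would improve the guess by an amount not worked out here. Without the arm, a non-responder looks like an ordinary placebo recipient. What remains open is that neither document says the codes are fixed before unblinding.

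Third, the 5% trigger counts exclusions under all codes, and SAP Template 4 plans a table of ATP exclusions with reasons. Both reduce the chance that this passes unseen, but neither guarantees a GMC ratio with these women retained. Finally, Protocol 6.8 and SAP code 2060 already allow elimination for pertussis infection, so not every rise in a placebo recipient would otherwise stay in the cohort.

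**Conclusion.** The defect holds: as written, SAP 5.2.1.1 permits exclusion from the primary cohort on the primary outcome, under a term that is undefined, not in Protocol 10.4.3 or SAP 5.1.3, and not declared in SAP Section 9.

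Neither the direction nor the size is established. Upward bias needs knowledge or a good guess of the arm. The 11% figure is a worst case: anti-PT only, a true ratio of exactly 1.5, perfect arm knowledge, and trimming of cord values rather than change. It should not be read as the trial's type I error. The 5.5% figure rests on the assumed correlation of 0.6. Under blind application the ratio falls to about 1.37–1.48 and the false-positive rate to 1.8% or less.

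At the planned ratios (2.3, 5 and 5), a few exclusions would be unlikely to change the conclusion. The point bites mainly if the observed anti-PT ratio lies near 1.88. The change is still worth making, because it removes selection on the endpoint at almost no cost.

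**What to change.** In SAP 5.2.1.1, delete the second of the three grounds in code 2120. Limit the code to sample or data errors documented from records other than the concentration, such as a label or CRF/laboratory mismatch, and state that codes are assigned before unblinding. Keep verified but unexpected results in the primary cohort.

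If the ground is kept, run the primary cord GMC ratios with all such women retained, whatever the 5% trigger says, and report code 2120 counts by arm.

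The cost is SAP wording, plus one table if the ground stays. The downside is that an undetected sample swap may remain in the data. A swap between arms dilutes the ratio, which is conservative for a superiority claim.

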### **5.3. Important protocol deviation not leading to elimination from per-protocol analysis set**

Refer to the protocol deviation management plan for important protocol deviation not leading to elimination from ATP cohort for immunogenicity.

## **6. STATISTICAL ANALYSES**

Note that standard data derivation rule and stat methods are described in section 11 and will not be repeated below.

### **6.1. Demography**

#### **6.1.1. Analysis of demographics/baseline characteristics planned in the protocol**

Demographic characteristics (age at the booster dose in years, race, height [cm], weight [kg], body mass index in kg/m^2), cohort description and withdrawal status will be summarised by group using descriptive statistics:

- Frequency tables will be generated for categorical variables such as race;
- Mean, median and standard error will be provided for continuous data such as age.

The distribution of subjects enrolled among the study sites and countries will be tabulated as a whole and per group.

Summary statistics by height [cm], weight [kg], head circumference [cm], body mass index [BMI in kg/m^2] and Apgar score of the infant will be tabulated as a whole and per group.

##### **6.1.1.1. Analysis of eligible household contacts**

Analysis of eligible household contacts will be performed on the Total cohort for household contacts in Spain.

- Demographic characteristics (age, sex, and race) will be summarised for the eligible household contacts as a whole and per group using descriptive statistics.
- Reasons for refusal of the cocooning vaccination will be summarised for the eligible household contacts as a whole and per group.
- Percentage of household contacts of the infants born to pregnant women vaccinated in Spain who accepted *Boostrix* vaccine as part of an assessment of cocooning among the eligible household contacts will be tabulated as a whole and per group.

##### **6.1.2. Additional considerations**

Breast feeding status, gestational age at vaccination and the time between vaccination and delivery will be summarised as a whole and per group using descriptive statistics.

The total number of household contacts approached, summary statistics for the number of household contacts by vaccinated subject will be generated in the subset of subjects in Spain.

Note that for a few of the household contacts, since they were later on classified as eligible based on the reasons for refusal, their demographic information is missing.

Apgar score will be summarized at 1 minute and 5 minutes post vaccination. No summary will be provided at 10 minutes as the measurement is optional.

## **6.2. Exposure**

The number of pregnant mother vaccinated will be provided by study group and refer to section 6.1.1.1 for exposure in household contacts.

## **6.3. Immunogenicity**

### **6.3.1. Analysis of immunogenicity planned in the protocol**

The primary analysis will be based on the ATP cohort for analysis of immunogenicity. If, in any vaccine group, the percentage of vaccinated subjects with serological results excluded from this ATP cohort is 5% or more, a second analysis based on the TVC will be performed to complement the ATP analysis.

#### **6.3.1.1. Within group assessment:**

For each treatment group, before and one month after vaccination during pregnancy and if blood sample result is available:

- Seroprotection rates and their exact 95% CIs for antibodies against diphtheria and tetanus will be calculated.
- Seropositivity rates and their exact 95% CIs for antibodies against PT, FHA, PRN, will be tabulated.
- GMCs and their 95% CIs for antibodies against all vaccine antigens will be calculated.
- The distribution of antibody concentrations pre, one month after booster vaccination for each antigen will be displayed using reverse cumulative distribution curves.
- Vaccine response to diphtheria, tetanus and pertussis antigens and their exact 95% CI will be calculated.

In the cord blood sample, if the blood sample result is available:

- Seropositivity rates and their exact 95% CIs for antibodies against PT, FHA, PRN, will be tabulated.
- GMCs and their 95% CIs for antibodies against PT, FHA, PRN antigens will be calculated.

**6.3.1.2. Between group assessment:**

- The primary objective is to demonstrate that, the immune response in the dTpa Group is superior to that in the Control Group for the pertussis antigens, in the cord blood sample.
  - *The LL of the 95% CI of the GMC ratio [dTpa Group divided by Control Group] for anti-PT, anti-FHA and anti-PRN antibodies are  $\geq 1.5$ .*

The CI of the group GMC ratios will be computed using a two-sample t test assuming heterogeneity of variance.

**6.3.2. Additional considerations**

Percentage of subjects with anti-D and anti-T antibody concentrations  $\geq 1.0$  IU/ml will be calculated along with its exact 95% CI by vaccine group at each visit.

For the distribution of antibody concentrations displayed using reverse cumulative distribution curves, the pre booster will also be included in the same graph as the one month after booster vaccination.

The distribution of antibody concentrations measured from the cord blood will also be generated in separated graphs.

The following descriptive analysis will be performed by sub-group of gestational age (27-32, 33-36 weeks of gestation of foetus at dose 1) and age of mother (18-24, 25-34, 35-45).

For each treatment group, before and one month after vaccination during pregnancy, cord blood sample and if blood sample result is available:

- Seroprotection rates and percentage of subjects with anti-D and anti-T antibody concentrations  $\geq 1.0$  IU/ml will be calculated along with and their exact 95% CIs for antibodies against diphtheria and tetanus.
- Seropositivity rates and their exact 95% CIs for antibodies against PT, FHA, PRN, will be tabulated.
- GMCs and their 95% CIs for antibodies against all vaccine antigens will be calculated.

## 6.4. Analysis of safety

### 6.4.1. Analysis of safety planned in the protocol

The primary analysis will be performed on the TVC. If in any vaccine group, 5% or more of the vaccinated subjects are eliminated from the TVC, a second analysis will be performed on the ATP cohort for analysis of safety. Analysis of safety in household contacts will be performed on the Total cohort for household contacts in Spain.

- The percentage of subjects with each specific pregnancy outcomes and listed pregnancy-related adverse events of interest/neonate-related events of interest will be tabulated with its exact 95% CI.
- The percentage of subjects with at least one local AE (solicited and unsolicited), with at least one general AE (solicited and unsolicited) and with any AE during the 8-day (Day 0–Day 7) follow-up period after the vaccination will be tabulated after each dose with exact 95% CI. The same calculations will be performed for any Grade 3 (solicited or unsolicited) symptoms, any causal relationship to vaccination and for any symptoms requiring medical attention.
- The percentage of subjects reporting each individual solicited local and general AE during the 8-day (Day 0–Day 7) follow-up period after booster vaccination will be tabulated with its exact 95% CI for each group.
- All computations mentioned above will be done for Grade  $\geq 2$  (solicited symptoms only) and Grade 3 symptoms, for symptoms considered related to vaccination (general symptoms only), for Grade 3 symptoms considered related to vaccination (general symptoms only) and for symptoms that resulted in a medically-attended visit.
- Occurrence of fever and related fever will be reported per 0.5°C cumulative temperature increments as well as the occurrence of Grade 3 fever ( $> 39.0^{\circ}\text{C}$  axillary temperature) with causal relationship to vaccination.
- Any large injection site reaction (defined as any local swelling with diameter  $> 100$  mm and/or any noticeable diffuse injection site swelling (diameter not measurable) and/or any noticeable increased circumference of the injected limb) onset within 8 days (Day 0–Day 7) after each vaccination will be described in detail.
- The verbatim reports of unsolicited symptoms will be reviewed by a physician and the signs and symptoms will be coded according to MedDRA. Every verbatim term will be matched with the appropriate Preferred Term. The percentage of subjects with unsolicited symptoms occurring within 31 days (Day 0–Day 30) with its exact 95% CI will be tabulated by preferred term. Similar tabulation will be done for Grade 3 unsolicited symptoms and for unsolicited symptoms possibly related to vaccination.
- The percentage of subjects who started to receive at least one concomitant medication (i.e. any medication, antipyretic medication, prophylactic antipyretics) during the 4-day and 31-day follow-up period after vaccination will be tabulated after each dose with exact 95% CI.

- SAEs and withdrawal due to AEs and SAEs following booster dose up to Visit 4 will be described in detail.
- All SAEs assessed as being possibly related to study participation occurring throughout the study period will be described.
- All SAEs assessed as being possibly related to a concurrent GSK medication occurring throughout the study period will be described.
- For the vaccinated household contacts in Spain, SAEs following *Boostrix* vaccination up to 30 days will be described in detail.

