2.2. Secondary objectives (Amended: 15 July 2015)

- To assess the safety of a single dose of *Boostrix* in pregnant women, administered during 27-36 weeks of gestation, in terms of the outcomes of pregnancy and listed pregnancy-related adverse events of interest/neonate-related events of interest up to study end (Visit 4).
- To assess the immunogenicity of a single dose of *Boostrix* administered during pregnancy in terms of seropositivity status for antibodies against pertussis, in the cord blood sample.
- To assess the immunogenicity of a single dose of *Boostrix* administered during pregnancy in terms of seroprotection/seropositivity status, vaccine response and GMCs for antibodies against diphtheria, tetanus and pertussis, one month post-vaccination.
- To evaluate the reactogenicity of a single dose of *Boostrix* administered during pregnancy and post-delivery in terms of solicited symptoms during the 8-day (Day 0 – Day 7) follow-up period after vaccination.
- To assess the safety of a single dose of *Boostrix* administered during pregnancy and post-delivery in terms of unsolicited symptoms during the 31-day (Day 0 – Day 30) follow-up period after vaccination and serious adverse events (SAEs) during the period from Visit 1 up to Visit 4.
- ***To assess the acceptance rate of a single dose of Boostrix among eligible household contacts of the infants born to pregnant women enrolled in Spain, as part of an assessment of cocooning.***
- ***To assess the safety of a single dose of Boostrix in terms of SAEs among the vaccinated household contacts of the infants born to pregnant women in Spain, as part of an assessment of cocooning, from the day of vaccination till 30 days after the vaccination.***

Refer to Section 10.2 for the definition of the secondary endpoints.

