10.8. Analysis of safety (Amended: 15 July 2015)

The primary analysis will be performed on the TVC. If in any vaccine group, 5% or more of the vaccinated subjects are eliminated from the TVC, a second analysis will be performed on the ATP cohort for analysis of safety. ***Analysis of safety in household contacts will be performed on the Total cohort for household contacts in Spain.***

- The percentage of subjects with each specific pregnancy outcomes and listed pregnancy-related adverse events of interest/neonate-related events of interest will be tabulated with its exact 95% CI.
- The percentage of subjects with at least one local AE (solicited and unsolicited), with at least one general AE (solicited and unsolicited) and with any AE during the 8-day (Day 0–Day 7) follow-up period after the vaccination will be tabulated after each dose and overall with exact 95% CI. The same calculations will be performed for any Grade 3 (solicited or unsolicited) symptoms and for any symptoms requiring medical attention.
- The percentage of doses followed by at least one local AE (solicited and unsolicited), with at least one general AE (solicited and unsolicited) and with any AE during the 8-day (Day 0–Day 7) follow-up period after the vaccination will be tabulated with exact 95% CI. The same calculations will be performed for any Grade 3 (solicited or unsolicited) symptoms and for any symptoms requiring medical attention.
- The percentage of subjects/doses reporting each individual solicited local and general AE during the 8-day (Day 0–Day 7) follow-up period after booster vaccination will be tabulated with its exact 95% CI for each group.
- All computations mentioned above will be done for Grade ≥ 2 (solicited symptoms only) and Grade 3 symptoms, for symptoms considered related to vaccination (general symptoms only), for Grade 3 symptoms considered related to vaccination (general symptoms only) and for symptoms that resulted in a medically-attended visit.
- Occurrence of fever and related fever will be reported per 0.5°C cumulative temperature increments as well as the occurrence of Grade 3 fever ($> 39.0^{\circ}\text{C}$ axillary temperature) with causal relationship to vaccination.

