## **7. ANALYSIS INTERPRETATION**

For analysis on the primary objective with pre-defined success criteria and an appropriate type I error control, appropriate conclusion can be drawn.

The secondary objectives of the study are descriptive and should be interpreted as such.

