## **11. ANNEX 1 STANDARD DATA DERIVATION RULE AND STATISTICAL METHODS**

### **11.1. Statistical Method References**

The exact two-sided 95% CIs for a proportion within a group will be the Clopper-Pearson exact CI [Clopper CJ, Pearson ES. The use of confidence or fiducial limits illustrated in the case of binomial. *Biometrika*. 1934;26:404-413].

The 95% CIs of the group GMC ratios will be computed using an ANOVA model on the logarithm10 transformation of the concentrations. The ANOVA model will include the vaccine group as fixed effects. The CI of the group GMC ratios will be computed using a two-sample Welch's t test assuming heterogeneity of variance.

The 95% CI for GMTs/GMCs will be obtained within each group separately. The 95% CI for the mean of log-transformed titre/concentration will be first obtained assuming that log-transformed values were normally distributed with unknown variance. The 95% CI for the GMTs/GMCs will then be obtained by exponential-transformation of the 95% CI for the mean of log-transformed titre/concentration.

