**Template 14 Percentage of subjects by pregnancy outcome (Total vaccinated cohort-Mother)**

	dTpa Group				Control Group			
	N =		95% CI		N =		95% CI	
Pregnancy outcome	n	Per	LL	UL	n	Per	LL	UL
Live infant NO apparent congenital anomaly								
Live infant congenital anomaly								
Elective termination NO apparent congenital anomaly								
Elective termination congenital anomaly								
Spontaneous abortion NO apparent congenital anomaly								
Spontaneous abortion congenital anomaly								
Stillbirth NO apparent congenital anomaly								
Stillbirth congenital anomaly								
Ectopic pregnancy								
Molar pregnancy								
Lost to follow-up								
Pregnancy ongoing								

dTpa group = Mothers received dTpa during pregnancy

Control group = Mothers received placebo during pregnancy

N = number of subjects with at least one administered dose

n/Per = number/percentage of subjects reporting a specific pregnancy outcome

95% CI= exact 95% confidence interval; LL = Lower Limit, UL = Upper Limit

**Template 15 Percentage of subjects with listed pregnancy/neonate related adverse events of interest (Total vaccinated cohort)**

Pregnancy-related adverse events of interest/neonate-related events of interest	dTpa Group N =				Control Group N =			
	n	%	Exact 95%CI		n	%	Exact 95%CI	
			LL	UL			LL	UL
Gestational diabetes								
Pregnancy-related hypertension								
Premature rupture of membranes								
Preterm premature rupture of membranes								
Premature labour								
Premature uterine contractions								
Intrauterine growth restriction/poor foetal growth								
Pre-eclampsia								
Eclampsia								
Vaginal or intrauterine haemorrhage								
Maternal death								
Preterm birth								
Neonatal death								
Small for gestational age								
Neonatal hypoxic ischaemic encephalopathy								
Failure to thrive/growth deficiency								

dTpa group = Mothers received dTpa during pregnancy

Control group = Mothers received placebo during pregnancy

N = number of subjects with at least one administered dose

n/Per = number/percentage of pregnancies/neonate with a specific adverse event

95% CI= exact 95% confidence interval; LL = Lower Limit, UL = Upper Limit

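### Pregnancy outcomes and listed events get only within-group exact CIs; a pre-specified descriptive risk difference with its CI should be added

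*SAP*

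**What the plan says.** The first secondary objective listed in Protocol 2.2 and SAP 3 is to assess safety through pregnancy outcomes and listed events up to Visit 4. The verb is assess, not compare.

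Protocol 10.8 and SAP 6.4.1 give the same analysis rule. In the SAP: "listed pregnancy-related adverse events of interest/neonate-related events of interest will be tabulated with its exact 95% CI". SAP 11.1 fixes the interval: "The exact two-sided 95% CIs for a proportion within a group will be the Clopper-Pearson exact CI". The only between-group method there is for immunogenicity: "The CI of the group GMC ratios will be computed using a two-sample Welch's t test assuming heterogeneity of variance".

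Templates 14 and 15 place dTpa and Control side by side, each with a count, a percentage and two limits. The footnote to Template 15 reads "n/Per = number/percentage of pregnancies/neonate with a specific adverse event". Neither shell has a column for a difference or a ratio. SAP 6.4.2 adds no contrast. SAP 11.2.7 has a general rounding rule for percentage differences and their limits, but no analysis or template shown uses it.

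On interpretation, SAP 7 says: "The secondary objectives of the study are descriptive and should be interpreted as such". Protocol 10.9 agrees.

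**The concern.** The trial has a concurrent randomised placebo group of about 340 women, and Protocol 1.2.1 names limited safety data in pregnancy as a reason for a controlled trial. Several listed events are common without any vaccine: Table 17 expects 36 of 300 for the hypertensive group, 35 of 300 for preterm delivery and 30 of 300 for growth restriction. At such rates a single-arm percentage says little about the vaccine. The informative quantity is the difference from Control.

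Two single-arm intervals do not give that quantity. Read by eye they can mislead, because two 95% CIs can overlap while the 95% CI of the difference excludes zero. When the arms look alike, they also leave unstated how large an excess remains compatible with the data. If no method is fixed in advance, anyone wanting the contrast chooses one after seeing the counts.

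**Working it through.** **Inputs.** N = 300 per group and the expected counts come from Protocol Table 17. The counts placed in two arms below are assumptions for illustration. Table 17 gives one expected count per event, not a scenario by arm, and 54 does not appear in it.

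**1. Reproduce the plan's figures.** Clopper-Pearson limits are the 0.025 quantile of Beta(x, n−x+1) and the 0.975 quantile of Beta(x+1, n−x). At n = 300:
- x = 0 gives an upper limit of 1.2%.
- x = 9 gives 1.4–5.6%.
- x = 36 gives 8.5–16.2%.

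These match Table 17. Eleven of its twelve rows reproduce. The exception is preterm delivery (35/300), where the upper limit computes to 15.9% against the printed 15.7%, which does not affect this point.

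**2. Equal arms, 36 against 36 (assumed).** The difference is 0. By the simple formula, SE = √(2 × 0.12 × 0.88/300) = 2.65 points, and 1.96 × 2.65 = 5.2. The Newcombe and Miettinen-Nurminen score intervals both give −5.3 to +5.3 points. The planned output would be 8.5–16.2% printed twice.

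**3. Unequal arms, 54 against 36 (assumed).**
- Within-group CIs: 54/300 = 18.0% (13.8–22.8) and 36/300 = 12.0% (8.5–16.2). They overlap.
- Difference: 6.0 points. SE = √(0.18 × 0.82/300 + 0.12 × 0.88/300) = √(0.000492 + 0.000352) = 2.905 points.
- 6.0 ± 1.96 × 2.905 = 0.3 to 11.7 points. Newcombe also gives 0.3 to 11.7; Miettinen-Nurminen gives 0.3 to 11.8.

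**4. Other Table 17 rates.** The second column assumes equal counts in both arms. The third gives the counts in the other arm for which the exact CIs overlap while the Newcombe CI of the difference excludes zero.

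| Count per 300 in one arm | 95% CI of difference if arms are equal (points) | Other-arm counts with overlap but difference excluding zero |
|---|---|---|
| 9 (major congenital anomalies) | ±3.0 | 20–25 |
| 15 (gestational diabetes) | about ±3.6 | 28–34 |
| 30 (growth restriction) | ±4.9 | 47–54 |
| 36 (hypertensive group) | ±5.3 | 54–61 |

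The 54 against 36 example therefore sits at the edge of a band, and each of these rates has such a band.

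**5. Number of added intervals.** Template 14 has 12 rows, of which two (lost to follow-up, ongoing pregnancy) are administrative. Template 15 has 16. So 12 − 2 + 16 = 26. At nominal coverage with no true differences, about 26 × 0.05 = 1.3 would exclude zero by chance.

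**The case against.** The plan is coherent as it stands. The objective is worded as an assessment, the safety precision in Table 17 is single-group, the method is single-group, the shells match, and both documents call the secondary objectives descriptive. All of that stands: this is not an internal contradiction or an invalid method.

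A reader might infer that the randomised comparison is lost, or that the trial cannot say what excess it excludes. The documents do not support that. Templates 14 and 15 print counts and denominators for both arms, so anyone can compute a difference, and the SAP nowhere tells readers to judge by overlap. What is missing is a pre-specified estimate and method, not information. Nor do the documents rank this as the main safety objective. They also do not say that the placebo arm exists to isolate background obstetric rates: Protocol 1.2.3 justifies placebo by limited implementation of vaccination in pregnancy and the absence of an established active control.

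Two further objections shape the fix. The Total Vaccinated cohort is analysed by treatment received, so a difference computed there is not strictly by randomised group. And Control women receive Boostrix within 72 hours of delivery while follow-up runs to Visit 4, so the meaning of the contrast changes for later events.

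The independent committee can see unblinded data, and the separate list of final tables cited in SAP 10 is not among the documents. Committee review is oversight rather than a reported estimate, and nothing in the text reviewed specifies a contrast.

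**Conclusion.** The point holds as a worthwhile and inexpensive improvement. For pregnancy outcomes and listed events, only separate within-group CIs are planned, and no difference or ratio with a CI is pre-specified. At 300 per group the missing statement would be an interval of roughly ±3 to ±5 points for events expected in 3% to 12% of women, if the arms were equal. Under the assumed 54 against 36, overlapping intervals would accompany a difference CI that excludes zero. These sizes rest on assumed counts by arm and on Table 17's N.

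An unadjusted difference with its CI remains descriptive, so the descriptive label is no reason to leave it out. For outcomes as rare as stillbirth (0 or 1 expected per 300) it would add little beyond showing the imprecision.

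**What to change.** In SAP 6.4.1 and 11.1 and in Templates 14 and 15, add the risk difference (dTpa minus Control) with a 95% Miettinen-Nurminen score CI for each pregnancy outcome and each listed event. Leave out the administrative rows for lost to follow-up and ongoing pregnancy. Label the columns descriptive, with no hypothesis test and no multiplicity adjustment.

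Add two statements:
- Groups are formed by the treatment received at Visit 1 (Total Vaccinated cohort), with a version by randomised group if the two differ for any subject.
- For events with onset after the post-delivery dose, the contrast is Boostrix in pregnancy against Boostrix post-delivery, not vaccine against no vaccine.

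The cost is a few columns on data already collected, with no effect on the primary analysis. The downside is about 26 unadjusted intervals on partly overlapping events (for example the two membrane-rupture terms, or growth restriction and small for gestational age). One or more may exclude zero by chance, and the intervals for rare outcomes will be wide.
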